#### 5.1. Hypotheses and Decision Rules

The null hypothesis for the primary endpoint is:

$H_0$ : There is no difference in mean percent change from baseline in non-HDL-C at Week 24 between vupanorsen and placebo.

The study objective is treatment effect estimation and dose selection and therefore no formal decision rules for inferential purposes are planned. Each vupanorsen treatment group will be compared to the pooled placebo group, ie, placebo-adjusted LS-mean treatment effect for each dose will be reported along with 95% CI and p-value without adjustment for multiple comparisons to placebo.

The Mixed Model Repeated Measurements (MMRM) will be used as the primary statistical method to estimate the difference of treatment effect between each dose of vupanorsen versus placebo at Week 24. Statistical inference including effect size, p-value, 95% CI will be presented for primary and secondary endpoints respectively, with no adjustment for multiplicity.

Although an interim analysis will occur at Week 16, no formal hypothesis testing nor statistical inference will be conducted.

#### 5.2. General Methods

##### 5.2.1. Analyses for Continuous Endpoints

Continuous endpoints will be summarized using the following descriptive statistics: number of subjects, arithmetic mean, standard deviation, median, minimum, maximum. Other descriptive statistics such as standard error, 1st quartile, 3rd quartile, IQR, etc. will

be added where appropriate. They will be summarized and tabulated by treatment groups and visits (including the 12-week safety follow-up visits when available), for the observed data and (percent) change from baseline.

For graphical summaries, mean +/- standard error, LS-Mean +/- standard error will be plotted for the observed data, (percent) change from baseline over time by treatment groups.

For statistical efficacy analyses, an MMRM model featuring the hypothetical estimand will be applied to primary and secondary endpoints, as primary analyses. All eligible post-baseline visits up to and including the analysis visit will be included in the MMRM model, in which baseline value, treatment (categorical), visit (categorical) and interaction term of treatment (categorical) by visit (categorical) will be treated as fixed effects and an unstructured covariance matrix will be used to account for the correlation among visits. If a model convergence issue is encountered with unstructured covariance matrix, then a simpler covariance structure, such as Toeplitz or compound symmetry will be considered. The restricted maximum likelihood (REML) method along with Kenward-Roger adjustment for degrees of freedom will be used for parameter estimation.

In addition to the primary analysis, the following three supplementary analyses will be conducted for additional evaluation of the primary and key secondary endpoints (ie, evaluated at Week 24). The first two, one using the MMRM model and the other using the multiple imputation using retrieved dropouts (MI-RD) approach, based on the TP estimand will be applied to the FAS (ie, including data collected post occurrence of intercurrent events as defined in [Section 2.1.3.1](#)). The last one, will be conducted in the framework of the principal stratum estimand, with details to be described in [Section 5.2.1.1](#). One sensitivity missing data analysis ([Section 5.3](#)) under the assumption of missing not at random (MNAR) will be implemented to evaluate the robustness of the primary results, for primary and key secondary endpoints. As in the primary analysis, both supplementary and sensitivity analyses will report the estimates for treatment arms.

Apart from the above statistical efficacy analyses, a Bayesian dose-response model will be constructed to model the relationship between percent change from baseline at Week 24 and doses listed in [Table 3](#), along with estimated 95% CI, for each of the primary and selected key secondary endpoints ([Appendix 1](#)) respectively. The parameter estimates from the phase 2a study will inform the model estimation, ie, used as prior distribution of the 3 parameters (E0, Emax, ED50) and the standard deviation of the residual term.

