## 4. STUDY DESIGN

### 4.1. Overall Design

This is a multicenter, randomized, double-blind, placebo-controlled, dose-ranging, 8-arm parallel-group study in adults  $\geq 40$  years of age with dyslipidemia who are on a stable dose of a statin (with or without ezetimibe). Following the Screening Period to confirm eligibility, a total of approximately 260 participants will be randomized in the study to receive SC doses of vupanorsen or placebo administered Q2W or Q4W for the purpose of assessing efficacy, safety, and tolerability of vupanorsen. The total duration of treatment in the study is 24 weeks with an additional 12-week safety follow-up period.

The sponsor, along with academic leadership of the study (TIMI Study Group), will monitor the proportion of participants enrolled according to statin intensity to ensure that an adequate number of participants on high intensity statin are enrolled. High intensity statin use is defined as atorvastatin (40 mg or 80 mg per day) or rosuvastatin (20 mg or 40 mg per day). All other statin regimens are considered low or moderate intensity. Approximately 40% or more of participants enrolled should be on high intensity statin therapy, and enrollment of participants using low/moderate intensity statin may be capped.

Vupanorsen dosing will be accomplished by administration of 1 or 2 prefilled syringes of either 60 mg or 80 mg strength according to required total dose. Placebo will be provided as a prefilled syringe and will be administered as either 1 or 2 syringes. See Table 1 for the dosing plan.

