Since administration of 160 mg Q2W (total monthly dose of 320 mg) has not been studied previously, enrollment in this arm will be capped after 10 participants. Following unblinded data review by the E-DMC as described in the E-DMC charter, enrollment in this treatment arm may be re-opened for the remaining 30 participants or be stopped based on recommendation by the E-DMC. Separately, an interim analysis is planned and will also be reviewed by the E-DMC. The interim analysis will take place approximately 16 weeks after 50% of the planned participants (ie, approximately 110 participants), with exception of the 160 mg Q2W group, are randomized.

Efficacy and safety analyses will occur when all participants either complete 24 weeks of study participation or discontinue study participation. Additional summarizing of follow-up safety data will occur after the 12-week post-dose follow-up visit.

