### 9.2. Sample Size Determination

Assuming a common standard deviation of 17.5% (observed in the Month 6 data of the Phase 2a proof-of-concept and dose-ranging study) for the percent change from baseline in non-HDL-C at Week 24 and a treatment discontinuation rate of 15%, 20 participants per arm will correspond to a 95% CI of point estimate  $\pm 11.76\%$  for the difference of treatment effect (versus placebo). These parameters correspond to a power of 91.5% using a 2-sided alpha of 0.05, to detect a difference of -20%, without adjustment for multiple comparison to placebo.

A permutation block schedule will be used in enrollment within each arm, including vupanorsen and matching placebo. If enrollment is stopped for the 160 mg Q2W arm (see [Section 4.1](#)), the corresponding matching placebo enrollment will also be stopped.

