#### 6.4. Subset Analyses

Subgroup analyses of primary and key secondary endpoints (ie, at Week 24) will be performed, to check the consistency of conclusion of treatment effect within each category of the subgroup. The following subgroups will be analyzed:

- Baseline statin use (2 categories: high, low/moderate);
- Baseline TG level (< median, >=median);
- Baseline non-HDL-C level (<median, >=median);
- ADA status (positive, negative);
- BMI (<median, >=median).

FAS\_primary will be the analysis set of subgroup analyses. An ANCOVA model adjusting for baseline value, treatment (categorical), subgroup (categorical) and interaction term of treatment (categorical) by subgroup (categorical) will be applied. The p-value of the interaction term will also be reported.

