#### Appendix 4. Example SAS code

##### MMRM:

```
proc mixed data=adeff method=reml;
class subjid avisitn trt01pn;
model chg=base trt01pn avisitn trt01pn*avisitn/ddfm=kr s;
repeated avisitn/sub=subjid type=un;
run;
```

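### The two-stage 160 mg Q2W arm has no period-adjusted or concurrent-placebo analysis, and the MMRM leaves out statin intensity

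*SAP*

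**What the plan says.** **Model.** SAP 5.2.1 defines the primary MMRM: "baseline value, treatment (categorical), visit (categorical) and interaction term of treatment (categorical) by visit (categorical) will be treated as fixed effects". The example code in SAP Appendix 4 has the same terms: "model chg=base trt01pn avisitn trt01pn*avisitn/ddfm=kr s". Neither contains statin intensity or enrolment period.

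**Comparator.** SAP 5.1: "Each vupanorsen treatment group will be compared to the pooled placebo group".

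**Staged arm.** Protocol 4.1 and its Table 1 hold the 160 mg Q2W arm at 10 participants until the E-DMC has seen unblinded data. After that, "enrollment in this treatment arm may be re-opened for the remaining 30 participants or be stopped based on recommendation by the E-DMC". No other arm is paused. SAP 2.2 and SAP Table 1 do not mention the cap.

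**Allocation.** Protocol 9.2: "A permutation block schedule will be used in enrollment within each arm, including vupanorsen and matching placebo". If the 160 mg Q2W arm is stopped, "the corresponding matching placebo enrollment will also be stopped". The number of matching placebo participants per arm is not given, and no stratification by statin intensity is described.

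**Statin intensity.** Protocol 4.1 sets a trial-wide aim of roughly 40% or more on high-intensity statin and adds that "enrollment of participants using low/moderate intensity statin may be capped". SAP 6.4 lists it as a subgroup factor: "Baseline statin use (2 categories: high, low/moderate". That subgroup analysis is an ANCOVA with a treatment-by-subgroup interaction.

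**Other analyses.** The supplementary and sensitivity analyses in SAP 5.2.1, 5.3, 6.1.1.2 and Appendix 1 deal with intercurrent events and missing data. None deals with enrolment period or restricts placebo to participants enrolled at the same time.

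**The concern.** If the arm re-opens, up to 30 of its 40 participants (75%) enter in a second stage. The other arms, and the placebo in their blocks, may enrol right through the pause. The top-dose group can then be later, on average, than its comparator. Any change over calendar time in who is enrolled or how the study is run would become part of the estimated effect of that dose.

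The protocol itself contains features that can vary over time:
- the optional cap on low/moderate-intensity statin users (4.1);
- home visits and local laboratories for efficacy samples during a public emergency, expected to end when normal conditions return (Appendix 13);
- possible adaptation of the study after the interim analysis (9.5).

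The study's purpose is dose selection, and this is its highest dose. The same drift would reach the 320 mg point of the Bayesian Emax model, whose example code has no covariates.

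**Working it through.** **Inputs from the documents:** SD 17.5%, 15% discontinuation, planned difference −20% (Protocol 9.2); 260 randomised, of whom 40 are placebo and 40 are 160 mg Q2W; 10 before the pause and 30 after (Protocol 4.1, Table 1).

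**Assumptions:**
- matching placebo is split in proportion to arm size;
- the matching placebo pauses with its arm;
- the first 10 enrol alongside the first 25% of the other arms;
- retention is 85% in every cell;
- drift is a single additive step at re-opening, of 2 to 5 points. The documents give no drift size.

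Let f be the share of the other arms already enrolled at re-opening.

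**1. The plan's own figure.** 20 × 0.85 = 17 per arm. Half-width = 1.96 × 17.5 × √(2/17) = 11.76, and power for −20% is 91.5%. Both match Protocol 9.2.

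**2. The same formula for 40 versus 40.** 40 × 0.85 = 34 per arm. SE = 17.5 × √(2/34) = 4.24, half-width 8.32, power for −20% 99.7%.

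**3. Where the placebo comes from.** Active total is 260 − 40 = 220. Matching placebo for 160 mg Q2W = 40 × 40/220 = 7.3, so 40 − 7.3 = 32.7, about 33, belong to other arms' blocks. An equal split over seven arms gives 40/7 = 5.7 matching.

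**4. Late placebo and bias.**
- Late placebo = 0.75 × 7.3 + 32.7 × (1 − f).
- Bias = drift × (0.75 − late placebo/40).
- Placebo enrolled during the pause, so not concurrent with the arm = 32.7 × (f − 0.25).
- Type I error = Φ(−1.96 + bias/4.24) + Φ(−1.96 − bias/4.24).

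| f | Late placebo | Placebo enrolled in pause | Bias, drift 2 | Bias, drift 5 | Two-sided type I error, drift 5 |
|---|---|---|---|---|---|
| 0.50 | 21.8 (55%) | 8.2 (20%) | 0.4 | 1.0 | 5.7% |
| 0.75 | 13.6 (34%) | 16.4 (41%) | 0.8 | 2.0 | 7.7% |
| 1.00 | 5.5 (14%) | 24.5 (61%) | 1.2 | 3.1 | 11.2% |

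If there is no pause (f = 0.25), the late shares are equal and the bias is zero. More than half of placebo is non-concurrent only if f exceeds 0.25 + 20/32.7 = 0.86.

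**5. Cost of a period term.** The SE comes from a linear model with arm and period over all arms, weighted by retained cell counts.

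| f | SE | Half-width | Power for −20% |
|---|---|---|---|
| 0.50 | 4.27 | 8.37 | 99.7% |
| 0.75 | 4.38 | 8.59 | 99.5% |
| 1.00 | 5.40 | 10.58 | 96.0% |

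The last row can be checked by hand, because at f = 1 only this arm and its matching placebo are late. The two periods carry weights 10 × 34.5/44.5 = 7.76 and 30 × 5.45/35.45 = 4.62. The sum × 0.85 = 10.5, and SE = 17.5/√10.5 = 5.40.

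**6. Matching placebo alone.** About 7.3 × 0.85 = 6.2 retained. Half-width = 1.96 × 17.5 × √(1/34 + 1/6.2) = 15.0, power about 74%. This is too imprecise to serve as the remedy.

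**7. If the arm never re-opens.** 10 × 0.85 = 8.5 retained. Half-width = 1.96 × 17.5 × √(1/8.5 + 1/34), about 13. There is then no second stage. The 10 would still face some later-enrolled placebo, but at that precision it matters little.

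**The case against.** **Re-opening time is open.** Nothing says when the E-DMC review takes place or that the other arms fill first. Protocol 4.1 describes the interim analysis as separate, so its timing does not supply the answer. A reader might infer that the pooled placebo is largely non-concurrent with this arm. The documents do not support that: it needs f above about 0.86, and even at f = 1 about 39% of placebo is concurrent. Placebo from another arm's block is still concurrent if it is enrolled in the same period. This objection stands, which is why the size is given as a range.

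**The statin cap is optional and trial-wide.** A reader might infer that the enrolment rules make this arm differ by design in statin mix. They do not. A difference arises only if the arm re-opens, the cap is used, and the cap falls after much of the other enrolment. The arm also has its own matching placebo. This stands too.

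**Statin intensity is already in the plan.** The subgroup ANCOVA contains it, and the baseline lipid value in the MMRM may absorb part of a statin-related difference. This stands in part. The subgroup model examines effect modification and leaves the primary contrast unadjusted, and neither term deals with period. The documents do not show that statin intensity predicts percent change.

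**The bias is modest and the drift is assumed.** At worst 3.1 points is about 15% of the planned 20-point difference, in one of seven contrasts, in a study with no formal decision rules. This is fair and limits the point to a minor one.

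**Conclusion.** The gap is real but narrow. The plan compares a two-stage arm with a pooled placebo group and has no period-adjusted or concurrent-placebo analysis. The primary MMRM also leaves out statin intensity, which the sponsor monitors during enrolment.

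Under the assumptions above, a drift of 2 to 5 points biases the 160 mg Q2W contrast by between 0.4 and 3.1 points, depending on when the arm re-opens. The half-width is about 8.3. The placebo split, the re-opening time and the drift are all assumed; the documents fix none of them. The other six contrasts are affected only slightly, through late matching placebo in the common comparator. If the arm is not re-opened, the concern largely disappears.

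This is a cheap improvement. It does not invalidate the primary analysis.

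**What to change.** In SAP 5.2.1 (with the code in Appendix 4 and the table in Appendix 1):

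1. Add baseline statin intensity (high versus low/moderate) as a fixed effect in the MMRM. This costs one model degree of freedom, and SAP 6.5.1 already summarises the variable.
2. If the 160 mg Q2W arm re-opens, prespecify before unblinding a sensitivity MMRM for that contrast with enrolment period (before versus after re-opening) as a further fixed effect. Period follows from the randomisation date.
3. Keep period out of the primary model. Period and arm become collinear when re-opening is late, so the term costs most precision where the possible bias is largest.

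The cost is one extra analysis. Its half-width for this contrast would be about 8.4 to 8.6 if re-opening comes at 50% to 75% of the other enrolment, and about 10.6 if it comes only once the other arms are full.

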#### **2.2.4.1. Clinical Pharmacokinetics**

Concentrations of total full-length oligonucleotide in plasma, including the parent compound vupanorsen, its full-length oligonucleotide metabolites with 1, 2, and/or 3 GalNAc sugar deletions and unconjugated vupanorsen, were quantitated as they are all potentially pharmacologically active. For simplicity, vupanorsen concentration refers to all full length oligonucleotides in the context of PK.

In the Phase 1 study, following single-dose or multiple-dose SC administration, vupanorsen was absorbed rapidly into the systemic circulation, with median  $T_{max}$  ranging from 1 to 8 hours. After reaching  $C_{max}$ , plasma concentrations of vupanorsen declined in a multi-phasic fashion with a rapid disposition phase, followed by a slower elimination phase with mean terminal elimination half-life of 3 to 5 weeks.  $C_{max}$  and AUC increased approximately dose proportionally from 20 mg to 120 mg after a single SC dose, and from 10 mg to 60 mg after

single and multiple weekly SC doses. No accumulation was observed based on  $C_{\max}$  and AUC after weekly doses. Plasma trough concentrations indicated that steady-state was not reached after 6 weeks of weekly dosing, consistent with the observed long half-life of the drug.

Vupanorsen PK profiles were evaluated in a subset of participants in the Phase 2a study. Following 20 mg QW, 40 mg and 80 mg Q4W SC dosing, the observed preliminary vupanorsen PK in the Phase 2a study were consistent with those in the Phase 1 study. Plasma trough concentrations appeared to reach steady-state after 21 weeks of dosing. The presence of ADA showed no apparent impact on  $C_{\max}$  and AUC, but increased plasma trough concentrations based on preliminary analysis.

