#### **9.4.3. Secondary Endpoint(s)**

No multiplicity adjustments will be applied to secondary endpoints. All secondary endpoints will be primarily analyzed using the FAS\_Primary analysis set.

For continuous secondary endpoints, MMRM analyses will be implemented, with both LS-mean and placebo-adjusted LS-mean along with 95% CI, p-value at Weeks 4, 8, 12, 16, 20, and 24 estimated. The same type of Bayesian  $E_{\max}$  dose-response model will be estimated using the FAS\_Primary analysis set for each of the key secondary endpoints respectively. Sensitivity analyses will also only be performed on key secondary endpoints (details are covered in the SAP).

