### **6.3. Other Endpoint(s)**

#### **6.3.1. Safety Endpoints**

The following will be summarized according to [Section 5.2](#), using the safety analysis set defined in [Section 4.2](#).

- Incidence of treatment-emergent SAEs and AEs throughout the study.
- Incidence of AESI.
- Categorical summaries of clinical laboratory abnormalities:
  - ALT/AST abnormalities:
    - Value  $\geq 3$  x ULN;
    - Value  $\geq 5$  x ULN;
    - Value  $\geq 8$  x ULN.
  - Percent reduction from baseline in eGFR  $\geq 40\%$ .
  - Platelet abnormality:
    - Confirmed platelet counts  $< 100,000$ ;

- Confirmed platelet counts <75,000;
- Confirmed platelet counts <50,000.
- Platelet count changes:
  - Percent reduction from baseline in platelet counts  $\geq 30\%$ ;
  - Percent reduction from baseline in platelet counts  $\geq 50\%$ .
- UACR;
- ADA.

*Immunogenicity of vupanorsen will be assessed before, during, and after treatment. A listing of individual plasma ADA results (including ADA positive, negative, and unknown status samples and titers) sorted by treatment group, participant ID, planned visit, and the visit date/time will be reported. The incidence (number) and incidence rate (percent) of ADA positive, negative and unknown participants will be summarized by treatment group and planned visit and for the overall study. The ADA positive (ADA+) participants will be further subcategorized into TEADA if the baseline ADA is negative. The incidence and incidence rate of TEADA will be summarized by treatment group and planned visit and for the overall study.*

- ECG (Section 9.4.5.1. of the protocol);
- Vital signs (BP and pulse rate).

The following will be summarized and (percent) change from baseline will be analyzed according to [Section 5.2](#), using the safety analysis set:

- AST;
- ALT;
- Platelet counts;
- eGFR;
- Hepatic fat fraction;
- UACR.

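### If the unstructured MMRM does not converge, the fallbacks named in SAP 5.2.1 would base the Week 24 standard error on a variance pooled over Weeks 4 to 24

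*SAP*

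**What the plan says.** SAP Section 5.2.1 sets out the primary model. On the data that enter it: "All eligible post-baseline visits up to and including the analysis visit will be included in the MMRM model". On the covariance: "an unstructured covariance matrix will be used to account for the correlation among visits". If that model has a convergence problem, "then a simpler covariance structure, such as Toeplitz or compound symmetry will be considered". On estimation: "The restricted maximum likelihood (REML) method along with Kenward-Roger adjustment for degrees of freedom will be used for parameter estimation".

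The modelled visits for the lipid endpoints are Weeks 4, 8, 12, 16, 20 and 24. Protocol Section 9.4.3 asks for estimates with "p-value at Weeks 4, 8, 12, 16, 20, and 24 estimated", and the on-treatment visit windows in SAP Appendix 2.1 are the same six. The example code in SAP Appendix 4 shows only the unstructured case ("repeated avisitn/sub=subjid type=un"), with no fallback code and no empirical standard error option.

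The result reported from this model (SAP Section 6.1.1.1) is the difference in LS means between each vupanorsen group and placebo, with its 95% CI and p-value. For the primary endpoint this is a contrast at one visit, Week 24.

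**The concern.** An unstructured matrix gives each visit its own variance, so the Week 24 contrast gets a standard error tied to the Week 24 spread. Standard Toeplitz and standard compound symmetry relax the correlation pattern, but they also impose one variance on every visit. The Week 24 standard error is then driven by a variance pooled over all six visits. Kenward-Roger does not repair this, because it adjusts within the assumed covariance model, and the plan provides no robust standard error.

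SAP Section 5.1 gives the study objective as effect estimation and dose selection, so interval width is a main product of the trial. If the spread at Week 24 is larger than at earlier visits, the fallback intervals would be too narrow. If it is smaller, they would be too wide. The sample size rests on the Month 6 SD alone, so nothing in the documents supports equal variances over visits.

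**Working it through.** **The plan's own figure.** Inputs from Protocol Section 9.2: SD 17.5, 20 per arm, 15% discontinuation, so 20 × 0.85 = 17 per arm.

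- SE = 17.5 × √(1/17 + 1/17) = 6.00; half-width = 1.96 × 6.00 = 11.76, as stated.
- Power for a difference of 20 = Φ(20/6.00 − 1.96) = Φ(1.37) = 91.5%, as stated.

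The plan's precision is therefore scaled to the Month 6 (Week 24) SD.

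**Effect of a common variance.** With complete data, the compound symmetry variance is the mean of the six visit variances, so

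- pooled SD = √(mean of the six squared SDs)
- SE ratio = pooled SD / 17.5
- coverage of a nominal 95% CI = 2Φ(1.96 × SE ratio) − 1

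No SD before Week 24 is given, so the visit profile is an assumption. For a linear rise from 80% of 17.5 at Week 4:

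- SDs: 14.0, 14.7, 15.4, 16.1, 16.8, 17.5
- Squares: 196.00, 216.09, 237.16, 259.21, 282.24, 306.25; sum 1496.95; mean 249.49
- Pooled SD 15.80; SE ratio 15.80/17.5 = 0.903; coverage 92.3%
- Half-width with 20 per arm and complete data: 1.96 × 15.80 × √(2/20) = 9.79, against 1.96 × 17.5 × √(2/20) = 10.85 with a separate Week 24 variance

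**Range over the assumed Week 4 SD (as a share of the Week 24 SD).** The concave profile follows an approach to steady state with the half-life of 3 to 5 weeks in Protocol Section 2.2.4.1. With F(t) = 1 − 2^(−t/h) and h = 3 to 5, SD(t) = 17.5 × [r + (1 − r)(F(t) − F(4))/(F(24) − F(4))].

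| Week 4 share r | SE ratio, linear | Coverage, linear | Coverage, concave |
|---|---|---|---|
| 1.0 | 1.00 | 95.0% | 95.0% |
| 0.9 | 0.95 | 93.8% | not tabulated |
| 0.8 | 0.90 | 92.3% | 93.3% to 93.7% |
| 0.7 | 0.86 | 90.7% | 92.4% to 93.0% |
| 0.6 | 0.81 | 88.8% | 91.4% to 92.4% |

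If the Week 4 SD is instead 10% to 30% above the Week 24 SD, with a linear fall, the interval is about 5% to 15% too wide.

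**Check by likelihood.** Each structure was also fitted by maximising the expected Gaussian likelihood under unequal visit variances, with assumed correlations falling from 0.70 at one visit apart to 0.50 at five. For SDs from 14 to 17.5 with complete data, the half-widths are 9.79 (compound symmetry) and 9.80 (Toeplitz), so the two structures behave almost alike. With 15% monotone dropout they are 10.14 and 10.23, against 11.40 under the true covariance (ratios 0.89 and 0.90). With equal variances the ratio is 1.00 with complete data, and 0.99 for compound symmetry with dropout.

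**How likely the trigger is.** Six visits give 6 × 7/2 = 21 covariance parameters, estimated from about 260 participants. Non-convergence is unlikely.

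**The case against.** The strongest reply is that this clause will probably never be used, and that harm cannot be shown even if it is. Both parts stand. The unstructured lipid model should converge, and no document gives an earlier-visit SD. A reader might infer that every Week 24 interval would be wrong under the fallback. That does not follow: with equal variances there is essentially no error.

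A reader might also infer a rising spread from the pharmacokinetics, since "Plasma trough concentrations appeared to reach steady-state after 21 weeks of dosing". That sentence concerns plasma trough levels, not between-participant variance in lipid response. The same section reports no accumulation in Cmax or AUC after weekly doses, and placebo participants have no drug build-up at all. It makes a changing spread plausible in the active arms and no more. If spread did follow that curve, the concave column applies and the error is smaller.

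A third tempting inference concerns the safety laboratory endpoints, for which SAP Section 6.3.1 says: "The following will be summarized and (percent) change from baseline will be analyzed according to" Section 5.2. Chemistry and hematology have nine scheduled post-baseline draws through Week 24, which would mean 9 × 10/2 = 45 parameters and a likelier failure. The documents do not define such a model. SAP Appendix 2.1 has six on-treatment windows: Day 8 falls in none, Day 15 falls in the Week 4 window and Day 43 in the Week 8 window. SAP Section 5.2.1 ties its MMRM to the primary and secondary efficacy endpoints. Protocol Section 9.4.1 does apply MMRM to continuous endpoints generally, but without a nine-visit specification.

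Nor does the SAP say that the structure would be chosen on unblinded data. The trigger is convergence, and choosing between the two named structures barely moves the standard error.

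Finally, the wording is open enough to allow heterogeneous versions, and SDs by visit will be tabulated. The return-to-baseline and retrieved-dropout analyses use ANCOVA on Week 24 values, and the principal stratum analysis uses a bootstrap. These are partial safeguards, because they answer under other assumptions or estimands. The open wording permits a better structure without committing to one.

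**Conclusion.** The point holds as a minor, conditional weakness in the specification. If the unstructured model fails and either named structure is used in its standard form, the Week 24 SE, CI and p-value rest on a variance pooled over Weeks 4 to 24, and are miscalibrated to the extent that spread differs by visit. Pooling is exact for compound symmetry with complete data and a close weighted average otherwise.

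Direction and size cannot be established from the documents. The figure of about 0.90 for the SE ratio and 92% for coverage rests on an assumed linear rise from 80% of the Week 24 SD and is illustrative only. The planned sample size is unaffected. The SAP plans no formal decision rules, so the consequence is for interval width in dose selection, not for a confirmatory test.

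**What to change.** Replace the fallback sentence in SAP Section 5.2.1 with a fixed order that always keeps a separate Week 24 variance: unstructured; then heterogeneous Toeplitz; then heterogeneous AR(1); then heterogeneous compound symmetry. Use the first that converges, with REML and Kenward-Roger retained, and report which one was used. Exclude structures with equal variance across visits. Add a closing clause for the case where none converges, for example the Week 24 ANCOVA on baseline and treatment that SAP Section 5.3 already uses, identified as such. Add the corresponding covariance types to the code in Appendix 4.

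The cost is a sentence or two and a few lines of code, with no change to design, conduct or sample size. If a fallback is used, six visit variances replace one, so five more parameters are estimated: 11 instead of 6 for Toeplitz and 7 instead of 2 for compound symmetry. Both remain well below the 21 of the unstructured matrix.
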